#### **5.8 Participant Withdrawal or Termination**

##### **5.8.1 Reasons for Withdrawal or Termination**

Participants are free to withdraw from participation in the study at any time upon request, without prejudice to their medical care. The reason for a patient's withdrawal or termination will be recorded in an electronic case report form (eCRF). The potential reasons could be:

CONFIDENTIAL

This material is the property of the NYU School of Medicine and Langone Medical Center. Do not disclose or use except as authorized in writing by the study sponsor

- Withdrawal of Consent by Participant
- Lost to Follow-up

Discontinuation of treatment is not a withdrawal of participation from the study. If treatment is discontinued, the participant should remain in the study and continue to be assessed at the scheduled study assessments.

### 5.8.2 Handling of Participant Withdrawals or Termination

If a participant (or legally authorized representative who provided consent) notifies the study team about withdrawing participation from the study, the study team will make all efforts to collect data related to the primary and secondary endpoints.

The investigator will make reasonable efforts to obtain, at a minimum, survival data on all participants lost to follow-up. Before a participant is considered lost to follow-up, study team will use any combination of the following methods to ascertain vital status:

- Multiple phone calls to participant and/or their next-of-kin
- Send certified letters to known addresses
- Search medical records system for recent routine visits

The overall clinical care of this patient will not change as a result of participation in this study nor will it change should the patient be withdrawn for any reason.

### 5.9 Premature Termination or Suspension of Study

This study may be temporarily suspended or prematurely terminated if there is sufficient reasonable cause. Written notification, documenting the reason for study suspension or termination, will be provided by the suspending or terminating party to the Principal Investigator, funding agency, the IND sponsor and regulatory authorities. If the study is prematurely terminated or suspended, the PI will promptly inform the IRB and will provide the reason(s) for the termination or suspension.

Circumstances that may warrant termination or suspension include, but are not limited to:

- Determination of unexpected, significant, or unacceptable risk to participants
- Insufficient compliance to protocol requirements
- Data that are not sufficiently complete and/or evaluable
- Determination of futility

Study may resume once concerns about safety, protocol compliance, data quality are addressed and satisfy the sponsor, IRB and/or FDA.

Although Reata intends to complete the study, Reata reserves the right to discontinue the study at any time for clinical or administrative reasons, or if required by regulatory agencies. If Reata discontinues the study, all study drug will be discontinued and the investigator will be responsible for securing any alternative therapy to be administered, as appropriate.

## 6 Study Agent

### 6.1 Study Agent(s) and Control Description

Bardoxolone methyl (RTA 402) drug product information is shown in Table 2. Information about the placebo is shown in Table 3.

**Table 2: Bardoxolone Methyl Drug Product Information**

Description	Bardoxolone methyl capsule (5 mg, 15 mg)
--------------------	------------------------------------------

CONFIDENTIAL

This material is the property of the NYU School of Medicine and Langone Medical Center. Do not disclose or use except as authorized in writing by the study sponsor

Ingredients	Bardoxolone methyl Methacrylic Acid – Ethyl Acrylate Copolymer (1:1), Type A Silicified Microcrystalline Cellulose Hydroxypropyl Methylcellulose Lactose Monohydrate Sodium Lauryl Sulfate Colloidal Silicon Dioxide Magnesium Stearate Gelatin capsules Titanium Dioxide (capsule pigment)
Route of Administration	Oral

**Table 3: Placebo Information**

Description	Placebo for bardoxolone methyl capsule (size #4 and size #1)
Ingredients	Silicified Microcrystalline Cellulose Lactose monohydrate Magnesium Stearate Gelatin capsules Titanium Dioxide (capsule pigment)
Route of Administration	Oral

### 6.1.1 Acquisition

Study drug will be shipped directly to each site prior to the start of the study. Blinded ordering of supplies will be maintained via the IWRS. Shipping contact information will be managed within the IWRS. All requests will require client approval prior to shipment.

### 6.1.2 Formulation, Appearance, Packaging, and Labeling

The study drug will be supplied in tamper-evident sealed kits containing two high-density polyethylene (HDPE) bottles. The 20mg kit contains two (HDPE) bottles (1) 30ct 15mg bottle and (1) 30ct 5mg bottle. The 20mg dose is attained by taking 1 capsule from each bottle as directed. The 10mg kit contains two (HDPE) bottles (2) 30ct 5mg bottles. The 10mg dose is attained by taking 1 capsule from each bottle as directed. Each bottle will utilize foil induction-seal liners and a child-resistant closure. Each bottle of study drug will contain 30 capsules of 5 mg or 15 mg strength bardoxolone methyl or the matching placebo capsules. Each bottle will also contain a desiccant insert that must not be ingested. Labeling on each bottle will contain at minimum the following information:

- Protocol: s20-00591
- Product name and strength
- Caution: New Drug – Limited by Federal Law to Investigational Use
- Keep out of reach of children
- Control or lot number
- Store at 15° – 25°C (59° – 77°F)

CONFIDENTIAL

This material is the property of the NYU School of Medicine and Langone Medical Center. Do not disclose or use except as authorized in writing by the study sponsor

- Reata Pharmaceuticals, Inc., Irving, TX

### **6.1.3 Product Storage and Stability**

The stability of the drug product has been and is currently being evaluated in ongoing studies. Investigative sites must store the investigational product in a secure location with room temperature conditions of 15° - 25°C (59° - 77°F).

### **6.1.4 Preparation**

Patients will be administered one capsule from each bottle included in the study drug kit orally once a day beginning on Day 1 while the patient remains hospitalized. Patients unable to receive oral medications (e.g., due to intubation and/or mechanical ventilation) may receive the contents of the capsule through a nasogastric or orogastric tube flushed with water. Each dose of study drug should be administered at approximately the same time each day, preferably in the morning.

### **6.1.5 Dosing and Administration**

Please refer to Section 7.1.1.7 for details on study drug administration, which will be administered at the time points listed in [Table 1](#). Patients must be instructed to continue taking study drug once daily while hospitalized (until recovery) with an expected duration of 10 days. For patients who are still hospitalized for more than 10 days, treatment can be continued for a maximum treatment duration of 29 days.

### **6.1.6 Route of Administration**

Bardoxolone methyl will be administered orally. Patients unable to receive oral dosing will receive study drug via a nasogastric or orogastric tube.

### **6.1.7 Starting Dose**

Patients will be randomized 1:1 to either 20 mg of bardoxolone methyl or placebo.

### **6.1.8 Dose Adjustments/Modifications/Delays**

The investigator may choose to decrease the patient's dose to a lower dose (e.g., 20 mg to 10 mg), if clinically indicated. Reasons for dose de-escalation should be documented. Once a patient's dose has been reduced, dose re-escalation back to a higher dose is permitted.

### **6.1.9 Duration of Therapy**

Patients will receive study drug while hospitalized (until recovery) with an expected duration of 10 days. For patients who are still hospitalized for more than 10 days, treatment can be continued for a maximum treatment duration of 29 days.

### **6.1.10 Tracking of Dose**

Study drug administration should be recorded in patient source record.

## **6.2 Study Agent Accountability Procedures**

The investigator, or designee, will maintain a record of all study drug received, dispensed, and returned. Study drug bottles and any unused capsules from dispensed kits should be disposed as biohazardous waste. At the conclusion of the study or in an instance of planned study drug replacement, Reata or its designee will direct the site regarding the final disposition of study drug.

CONFIDENTIAL

## 7 Study Procedures and Schedule

### 7.1 Study Procedures/Evaluations

#### 7.1.1 Study Specific Procedures

##### 7.1.1.1 Informed Consent

Informed consent (see [Section Error! Reference source not found.](#)) must be obtained from the patient or the legally authorized representative (for patients who cannot consent, for example, those who are intubated) before any study-related procedures are performed, and again if there is a change in the study procedures that would affect the patient's willingness to participate.

##### 7.1.1.2 Inclusion/Exclusion

Inclusion and exclusion criteria must be reviewed as indicated in [Table 1](#). Patients must meet all of the inclusion and none of the exclusion criteria for entry in the study. Investigators should contact the Reata Medical Monitor or the Clinical Coordinating Center with any questions regarding eligibility prior to randomizing the patient on Day 1.

##### 7.1.1.3 Demographics and Baseline Disease Characteristics

Demographic data including sex, age, race, and ethnicity, will be collected as indicated in [Table 1](#). Baseline disease characteristics will be collected as indicated in [Table 1](#).

##### 7.1.1.4 Prior and Current Concomitant Medications

The name, dose, and frequency must be recorded for all medications that the patient is taking. Trade or generic drug names should be used where possible. Concomitant medications will be reviewed as indicated in [Table 1](#) and all changes will be recorded.

##### 7.1.1.5 Medical History

A complete medical history that includes all available medical history must be collected. Medical history will be recorded as indicated in [Table 1](#).

##### 7.1.1.6 Pregnancy Test

WOCBP will complete a pregnancy test as indicated in [Table 1](#), or at any time if pregnancy is suspected. Any patient who becomes pregnant during the study must discontinue taking study drug immediately. See Section 8.4.4 for a description of procedures to be followed in case of pregnancy.

##### 7.1.1.7 Study Drug Administration

Patients will be administered one capsule from each bottle included in the study drug kit orally once a day beginning on Day 1 while the patient remains hospitalized, as indicated in [Table 1](#). Each dose of study drug should be administered at approximately the same time each day, preferably in the morning. Patients unable to receive oral medications (e.g., due to intubation and/or mechanical ventilation) may receive the contents of the capsule through a nasogastric or orogastric tube flushed with water. A vomited dose must not be replaced. A double dose (e.g., missed dose from previous day and dose for current day) must not be taken.

#### CONFIDENTIAL

#### 7.1.1.8 SARS CoV-2 PCR Test

A sample will be collected from the patient to test for presence of viral load as indicated in [Table 1](#). At the screening visit, study team is required to confirm there is a positive SARS CoV-2 PCR test to satisfy the study's inclusion criteria. If feasible per local clinical care, SARS CoV-2 PCR test is requested to be collected at Day 15 or End of Treatment, whichever is earlier.

#### 7.1.1.9 In-person/Telephone Contact

Patients will have a follow-up on Day 29, regardless of treatment adherence and recovery status prior to Day 29, and a safety follow-up 60 days after randomization, which may be conducted by in-person visit (preferable) or telephone call (if there are quarantine and other restrictions). The call will include questions on health status including new adverse events, continuing adverse events, hospital visits, continued care, reinfection or death following exposure to bardoxolone methyl or placebo in the trial.

#### 7.1.1.10 Adverse Event Collection

All adverse events will be recorded as indicated in [Table 1](#).

#### 7.1.1.11 Clinical Status Assessment

Clinical status of the patient will be assessed as indicated in [Table 1](#). The assessment will include collection of data related to critical events and other data to support the safety reporting criteria set by the DSMB. An 11-category ordinal scale defined in Section 4.2.2.3 will be used to support data collection for the exploratory endpoint.

#### 7.1.1.12 Recovery Assessment

Each of the following patient recovery components will be assessed as indicated in Table 4:

- Alive (yes/no)
- Free of respiratory failure (yes/no)
- Free of RRT (yes/no)

#### 7.1.1.13 eGFR

The eGFR value will be calculated using the Chronic Kidney Disease Epidemiology Collaboration (CKD-EPI) equation:

$$\text{eGFR (mL/min/1.73 m}^2\text{)} = 141 \times \min(S_{\text{cr}}/\kappa, 1)^\alpha \times \max(S_{\text{cr}}/\kappa, 1)^{-1.209} \times 0.993^{\text{Age}} \times 1.018 \text{ [if female]} \times 1.159 \text{ [if black]}$$

Where the patient's age on the date of consent is used,  $S_{\text{cr}}$  is serum creatinine (mg/dL),  $\kappa$  is 0.7 for females or 0.9 for males, and  $\alpha$  is -0.329 for females or -0.411 for males. Min indicates the minimum of  $S_{\text{cr}}/\kappa$  or 1 and max indicates the maximum of  $S_{\text{cr}}/\kappa$  or 1.

#### 7.1.1.14 PaO2/FiO2 Ratio

PaO2/FiO2 ratio will be collected as indicated in [Table 1](#) and calculated by using the PaO2 from the arterial blood gas and then dividing by the estimated FiO2 for that oxygen delivery method (0.21 for room air, 0.21 + (oxygen flow rate \* 0.03) for nasal cannula, 0.80 for non-rebreather mask or the recorded FiO2 for non-invasive or invasive ventilation) ([Brown SM et al. Chest 2016;150:307-13](#)).

#### CONFIDENTIAL

## 7.1.2 Standard of Care Study Procedures

### 7.1.2.1 Vital Sign Measurements

Vital sign measurements include the patient's heart rate, respiration rate, and body temperature. Vital sign measurements should be taken as indicated in [Table 1](#). Data related to vitals signs will be used to calculate a National Early Warning Score (NEWS) at each assessment. If feasible, vital sign measurements will be taken during outpatient study visits.

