#### **2.4.1.1 Fluid Overload**

Similar to endothelin receptor antagonists (ERAs) in certain patient populations, including bosentan in advanced congestive heart failure and avosentan in advanced CKD, bardoxolone methyl treatment was found to be associated with an increased risk for fluid overload and heart failure hospitalizations in the BEACON trial, which enrolled patients with Stage 4 CKD (eGFR 15 to 29 mL/min/1.73 m^2) and type 2 diabetes (Chin, 2014). The overall increased risk for fluid overload and heart failure events with bardoxolone methyl appeared to be limited to the first three to four weeks after initiation of treatment. Patients with fluid overload events who were treated with intravenous diuretics generally resolved their symptoms. Elevated BNP and prior hospitalization for heart failure were identified as risk factors that contributed to increased risk for these events. For patients without these baseline characteristics, the risk for heart failure events among bardoxolone methyl- and placebo- treated patients was similar (2%) (Chin, 2014). The increased risk for these events from bardoxolone methyl treatment had also not been observed in six previous CKD studies, which were conducted mostly in patients with Stage 3b CKD (eGFR of 30 to 44 mL/min/1.73 m^2), patients with hepatic dysfunction or cancer, or healthy volunteers.

Subsequent studies, enrolling over 1500 patients, have employed risk mitigation procedures to reduce the potential for bardoxolone methyl-induced fluid overload. These procedures excluded patients with the identified risk factors and ensured close monitoring for fluid retention within the first month of treatment. Since these exclusions have been applied, no increased risk for acute fluid overload AEs with bardoxolone methyl has been observed. As such, BARCONA will exclude patients with known left ventricular ejection fraction (LVEF) <40% or prior hospitalization for heart failure to mitigate this risk.

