##### 4.2.1.1 Primary Endpoint

- Safety (e.g., frequency, intensity, and relationship to study drug of serious adverse events [including unexpected deaths], change from baseline in vital sign and laboratory assessments) at Day 29

CONFIDENTIAL

This material is the property of the NYU School of Medicine and Langone Medical Center. Do not disclose or use except as authorized in writing by the study sponsor

## 4.2.2 Phase 3

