### 4.2.2.2 Secondday Efficacy Endpoint (assessed at Day 29 unless stated otherwise)

- Number of renal replacement therapy (RRT)-free days
- Number of mechanical ventilation-free days
- All-cause mortality
- Proportion of subjects experiencing a deterioration from baseline (as defined by a 1-point worsening) to end of treatment or Day 29 (whichever comes first) in clinical status using an 11-category ordinal scale:
  - 0 – Uninfected; no viral RNA detected
  - 1 – Asymptomatic; viral RNA detected
  - 2 – Symptomatic; Independent
  - 3 – Symptomatic; assistance needed
  - 4 – Hospitalized; no oxygen therapy
  - 5 – Hospitalized; oxygen by mask or nasal prongs
  - 6 – Hospitalized; oxygen by NIV or High flow
  - 7 – Intubation & Mechanical ventilation;  $pO_2/FIO_2 \geq 150$  or  $SpO_2/FIO_2 \geq 200$
  - 8 – Mechanical ventilation  $pO_2/FIO_2 < 150$  ( $SpO_2/FIO_2 < 200$ ) or vasopressors
  - 9 – Mechanical ventilation  $pO_2/FIO_2 < 150$  and vasopressors, dialysis or ECMO
  - 10 – Death

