## 5 Study Enrollment and Withdrawal

### 5.1 Inclusion Criteria

In order to be eligible to participate in this study, an individual must meet all of the following criteria:

1. Laboratory-confirmed COVID-19 infection as determined by polymerase chain reaction (PCR)
2. Hospitalized patients that meets one of the following conditions:
  - a. Radiographic infiltrates by imaging (chest x-ray, CT scan, etc.); OR

CONFIDENTIAL

This material is the property of the NYU School of Medicine and Langone Medical Center. Do not disclose or use except as authorized in writing by the study sponsor

- b. At rest, blood oxygen saturation  $\leq$  94%; OR
  - c. Require supplemental oxygen; OR
  - d. Requiring non-invasive ventilation; OR
  - e. Requiring invasive mechanical ventilation for up to 2 days.
3. Age  $\geq$  18 years. Enrollment of patients  $\geq$ 70 years of age may be limited (e.g., comprise no more than 10% of all randomized patients), pending safety review by the DSMB and executive committee
  4. Participant or legally authorized representative is willing to give informed consent

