### **10.4.4 Safety Analyses**

Safety and tolerability are evaluated by AEs, SAEs, clinical laboratory test results, vital sign measurements, and PaO2/FiO2 ratio. All analyses of the safety data will be performed using the safety analysis set. Descriptive statistics are presented by treatment group assignment in the safety analysis set.

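### The vital signs named in 7.1.2.1 leave out blood pressure and oxygen saturation, and the protocol does not say which data will supply the NEWS it promises

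*Combined protocol and SAP*

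**What the plan says.** Section 7.1.2.1, which sits under standard-of-care procedures, defines the set: "Vital sign measurements include the patient's heart rate, respiration rate, and body temperature". It then says that data related to vital signs "will be used to calculate a National Early Warning Score (NEWS) at each assessment".

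Vital signs carry weight in two other places. The Phase 2 primary safety endpoint in 4.2.1.1 gives, among its examples, "change from baseline in vital sign and laboratory assessments) at Day 29". Section 10.4.4 says: "Safety and tolerability are evaluated by AEs, SAEs, clinical laboratory test results, vital sign measurements, and" the PaO2/FiO2 ratio.

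Table 1 has a single vital-sign row, marked from Screening to Day 60. It has no row for blood pressure, SpO2, level of consciousness or NEWS.

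**The concern.** A data form built from 7.1.2.1 as written would have three vital-sign fields. Change from baseline in vital signs, compared between arms in about 40 Phase 2 patients, would then describe heart rate, respiration rate and temperature. Blood pressure and oxygen saturation would be missing from that element in a trial of hospitalized COVID-19 patients, where resting saturation is itself an entry condition.

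Adverse event reporting may not fill the gap. A Table 1 footnote limits collection to serious events with a reasonable possibility of relation to study drug, whereas 7.1.1.10 and 8.3 take in all adverse events. On the footnote's reading, a non-serious fall in blood pressure or saturation would not be recorded as an event, and the measured values would be the main way to see a difference between arms.

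The NEWS sentence adds a second problem: a score is promised at each assessment, but nothing tells a site or a programmer which fields feed it. With about 20 sites, inputs that are not specified in advance may be recorded unevenly or not at all.

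**Working it through.** No sample size, power or event figure bears on this point, so the check compares sections of the text.

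**Step 1: where each measurement is specified.**

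| Measurement | Where it appears | Scheduled as a repeated measurement? |
|---|---|---|
| Heart rate, respiration rate, temperature | 7.1.2.1; vital-sign row of Table 1 | Yes, Screening to Day 60 |
| Blood pressure | Not named as a study measurement | No |
| Oxygen saturation | Inclusion condition in 5.1 ("At rest, blood oxygen saturation" of 94% or less); SpO2/FiO2 cut-offs in the ventilated categories of the scale in 4.2.2.2 | No row of its own |
| Oxygen support | Clinical status scale (4.2.2.2); delivery method, flow and FiO2 used in 7.1.1.14 | Yes, through the clinical status row, Screening to Day 60 |
| PaO2/FiO2 from arterial gas | 7.1.1.14; safety variable in 10.4.4 | Days 1, 3, 5, 8, 11, 15, 22 and End of Treatment; not marked at Day 29 or Day 60 |
| BNP | 7.1.2.2 | Yes, every visit from Day 1 to Day 60 |
| Level of consciousness | Not named as a study measurement | No |
| NEWS | 7.1.2.1 only | No row; in no endpoint or analysis |

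The count is three named vital signs, no listing of blood pressure as a study measurement, and no scheduled row for SpO2, level of consciousness or NEWS.

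**Step 2: the safety endpoint.** Sections 4.2.1.1 and 10.4.4 use vital signs without redefining them, so 7.1.2.1 governs both. The vital-sign element therefore has neither blood pressure nor saturation. Oxygenation enters 10.4.4 separately, through PaO2/FiO2. That measure is not marked at Day 29, the time point of the Phase 2 endpoint, unless End of Treatment falls on that day, when the End of Treatment schedule applies (footnote j).

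**Step 3: NEWS.** The documents do not give its components, so there are two cases:

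- If NEWS needs only the three named items, it can be computed and there is no NEWS gap.
- If it needs any further input, it cannot be computed from the named set. Oxygen support could be taken from the clinical status and PaO2/FiO2 data. SpO2 might be available for some ventilated patients. No source is given for blood pressure or level of consciousness.

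Step 2 holds in either case.

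**Step 4: ordinal categories 7 and 8.** The deterioration endpoint compares baseline with End of Treatment or Day 29, whichever comes first. PaO2/FiO2 is scheduled pre-dose on Day 1 and at End of Treatment, so a scheduled value exists at both ends. The SpO2/FiO2 alternative is needed only when the arterial gas is not done; in that case, no procedure names SpO2 as a value to record.

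**The case against.** The strongest reply is that the list is not expressly closed. Section 7.1.2.1 introduces the three items as things that vital signs include, and NEWS is to be built from data related to vital signs. A site might well record more. This stands as far as it goes: the text does not forbid other measurements. But nothing in the documents extends the list, and a safety endpoint should not depend on what sites choose to add.

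Several stronger readings are tempting, and the documents do not support them.

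- A reader might infer that NEWS can be obtained at no assessment, or put a fraction on its missing inputs. Without a component list, neither follows; the claim is conditional, as in step 3 above.
- A reader might infer that the DSMB would have no hemodynamic or oxygenation information by arm. Heart rate is listed, PaO2/FiO2 is a named safety variable, and vasopressor use is part of scale categories 8 and 9. Section 7.1.1.11 also has the clinical status assessment collect data for the DSMB's safety reporting criteria. The DSMB charter and analysis plan are separate documents, not available here.
- A reader might infer that fluid overload goes unmonitored and that body weight must be added. The phrase in 2.4.1.1, "ensured close monitoring for fluid retention within the first month of treatment", describes procedures in other studies. For this trial that section relies on excluding patients with low ejection fraction or a prior heart failure hospitalization, and BNP is scheduled throughout. A body-weight requirement does not follow.
- A reader might infer that categories 7 and 8 have no source value. Step 4 shows that they do, unless the scheduled gas is missed.

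It is also fair to say that vital signs are only one example within the Phase 2 safety endpoint, alongside serious adverse events, deaths and laboratory values.

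**Conclusion.** The point holds in a limited form. The only definition of vital signs omits blood pressure and oxygen saturation, so the vital-sign element of the Phase 2 primary safety endpoint and of the safety analyses omits them too. The NEWS commitment has no stated inputs. That the score cannot be computed from the named set rests on the assumption that NEWS needs at least one item beyond the three.

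The consequence is an incomplete safety measure and an underspecified data item. Other scheduled measurements cover part of the gap, but none supplies blood pressure. NEWS feeds no endpoint or analysis, and the primary efficacy analysis, power and type I error are untouched. This is an inexpensive improvement to safety data collection and does not threaten the trial's main conclusion.

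**What to change.** Amend 7.1.2.1 and the Table 1 vital-sign row to name blood pressure and SpO2, with the oxygen device or FiO2 at the time of the reading, alongside the three existing items. State the NEWS inputs and add any not yet listed, such as level of consciousness if the version intended uses it. If the score is not intended, delete the NEWS sentence. Have sites transcribe the values from the bedside chart at in-hospital visits; the existing if-feasible provision for outpatient visits can stay. Where no arterial gas is available, use the same SpO2 and FiO2 values to separate ordinal categories 7 and 8.

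The cost is a wording change and a few eCRF fields. No new procedure is needed, assuming that these values are already charted in routine inpatient care. The downside is slightly more data entry.
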